#### **9.4 Sample Size, Planned Interim Analysis, Adaptive Design, and Data Monitoring Committee**

Data from the open-label group will be summarized using descriptive statistics and not included in double-blind efficacy analysis.

In the double-blind group, the response rates in the treatment and control groups will be compared using a 1-sided hypothesis test. An O'Brien-Fleming error spending function will be used with two predefined interim analyses. The two interim analyses will occur after approximately 156 and 200 subjects have completed 24-hours of study drug administration. Prior to initiating these pre-planned analyses, the data for these subjects will have a minimum of their critical fields cleaned.

Using a total one-sided Type I error of 2.5%, critical values for the two interim and one final analysis are noted in Table 6.

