**Table 6: Interim Analysis Variables**

Analysis	# Subjects who completed the study anytime within 24 hours of study drug administration	One-sided Critical Value	Error Spend	Cumulative Error Spend
Interim 1	156 subjects	0.0073	0.0073	0.0073
Interim 2	200 subjects	0.0135	0.0083	0.0156
Final	242 subjects	0.0200	0.00935	0.025

In the double-blind group a Data Monitoring Committee (DMC) will be assembled to review the safety and efficacy data at various intervals of the study. Only the unblinded DMC will be privy to these interim analyses and may recommend the trial stop for early success or safety findings.

Likewise, at each interim analysis, Bayesian predictive probabilities for success at the maximum (N=242) sample size will be calculated. If the predictive probability of success is < 5%, then the DMC may recommend the trial stops for futility. These are non-binding futility analyses, e.g., the Type I error = 2.5% even without these futility analyses. The Bayesian predictive probabilities will use non-informative Beta (1/2, 1/2) priors for both unknown response rates and be conducted using the methodology described in Saville et al., 2014 (Clinical Trials).

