## 9.5 Sample Size Calculation and Power Considerations

The double-blind sample size was constructed to offer at least 85% power with a 20% effect.

Table 7 shows the power for a control group response rates ranging from 30% to 70% and assuming a 20% improvement in the treatment group.

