**Table 7: O'Brien-Fleming Power and Sample Size Power Calculation**

Control Response %	Treatment Response %	Probability of Stopping at 156 Subjects	Probability of Stopping at 200 Subjects	Probability of Stopping at 242 Subjects	Total Power	Expected N
0.3	0.5	0.48	0.19	0.19	0.86	193
0.4	0.6	0.44	0.22	0.19	0.85	195
0.5	0.7	0.48	0.19	0.19	0.86	193
0.6	0.8	0.56	0.18	0.16	0.90	187
0.7	0.9	0.70	0.16	0.10	0.97	175

Two-hundred and forty-two subjects with the described O'Brien-Fleming stopping rules ensures 85% power in the scenario of 60% vs. 40% and increases for other scenarios with 20% effect sizes.

Using the futility rules based upon predicted probabilities, when control and treatment group response rates are equal, the probability of early stopping is 88% and expected sample size is 171.

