## 9.7 Efficacy Analyses

### 9.7.1 Primary Efficacy Endpoint

The primary efficacy endpoint is defined as the number of subjects who did not require an IV anesthetic drug (a 3rd line treatment) for SE treatment within the first 24 hours after study drug initiation.

The primary efficacy analysis will be conducted over the mITT Set. The primary efficacy analysis will be conducted by using a logistic model that includes treatment group as a factor along with factors controlling for age, GCS, and history of epilepsy. One-sided tests will be performed and compared to the critical values shown in Section 9.4, thus ensuring overall 1-sided Type I error  $\leq 0.025$ .

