1 INTRODUCTION

The purpose of this statistical analysis plan (SAP) is to provide detailed descriptions of predefined methods to be used for efficacy and safety analyses for Protocol 1042-SE-2001. The latest version of the protocol at the time of the writing of this statistical analysis plan is Final Protocol (Amendment 3, 24 January 2019, Version 4.0).

The structure and content of this SAP provides sufficient detail to meet the requirements identified by the Food and Drug Administration (FDA) and International Conference on Harmonization (ICH) of Technical Requirements for Registration of Pharmaceuticals for Human Use (ICH): Guidance on Statistical Principles in Clinical Trials.¹ All work planned and reported for this SAP will follow international accepted guidelines published by the American Statistical Association² for statistical practice.

The following documents were also considered in preparation for writing this SAP:

- International Conference on Harmonization (ICH) E3 Guideline: Structure and Content of Clinical Study Reports³
- ICH E6 Guideline on Good Clinical Practice⁴
- ICH E8 General Considerations for Clinical Trials⁵
- ICH E9 Statistical Principles for Clinical Trials⁶

The SAP is a supplement to the study protocol, which should be referred to for additional details on study design, study conduct, and other operational aspects of the study.

The original protocol included a double-blind phase which was planned after an open-label lead-in to confirm the dose selected achieved an approximately targeted plasma concentration of ganaxolone in the target population and to collect safety, efficacy, and feasibility of ganaxolone administration. This SAP supersedes the statistical considerations identified in the protocol; where considerations are substantially different. This SAP covers analysis of data collected from the open-label. The double-blind phase will now be conducted as a separate phase 3 study. Therefore, some of the analyses described in the study protocol will not be conducted. Key efficacy, safety, and pharmacokinetic data are summarized, and no formal statistical tests are performed for inference. Subjects are categorized into three cohorts based upon target dose of study medication. Cohorts are:

- Cohort 1: High (Target dose of 713 mg/day)
- Cohort 2: Medium (Target dose of 650 mg/day)
- Cohort 3: Low (Target dose of 500 mg/day)

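### Table 6's critical values spend about 0.0259, not 0.025, at looks of 156, 200 and 242 subjects, and Table 7 does not follow from the 0.0135 second-look threshold

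*Protocol*

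**What the plan says.** Protocol 9.4 plans a one-sided comparison in which an O'Brien-Fleming "error spending function will be used with two predefined interim analyses". On timing: "The two interim analyses will occur after approximately 156 and 200 subjects have completed 24-hours of study drug administration". On error: "Using a total one-sided Type I error of 2.5%, critical values for the two interim and one final analysis are noted in Table 6".

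The entries listed there are:

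| Look | Subjects | Critical value | Error spend | Cumulative spend |
|---|---|---|---|---|
| Interim 1 | 156 | 0.0073 | 0.0073 | 0.0073 |
| Interim 2 | 200 | 0.0135 | 0.0083 | 0.0156 |
| Final | 242 | 0.0200 | 0.00935 | 0.025 |

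The futility rule is non-binding, and the text under Table 6 says that "the Type I error = 2.5% even without these futility analyses". Section 9.7.1 tests the primary endpoint with a logistic model whose one-sided tests are "compared to the critical values shown in Section 9.4, thus ensuring overall 1-sided Type I error" at or below 0.025.

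On power, 9.5 says: "The double-blind sample size was constructed to offer at least 85% power with a 20% effect". Table 7 gives stopping probabilities at 156, 200 and 242 subjects, total power and expected N for five control rates. The SAP (section 1) adds: "The double-blind phase will now be conducted as a separate phase 3 study".

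**The concern.** Once the look times are fixed, the critical values and the error spent determine each other. Table 6 gives all three, so it can be checked, and the columns do not agree. Section 9.7.1 rests its Type I error guarantee on the critical values, and non-binding futility cannot be counted on to offset an excess.

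Table 7 should be the operating characteristics of the rule in Table 6. If it was produced with a different second-look threshold, its look-by-look stopping probabilities and expected N describe another design. Anyone carrying these boundaries into a later trial would inherit both problems.

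**Working it through.** **Inputs.** Looks 156, 200 and 242 (9.4, Table 6) give information fractions t = 156/242 = 0.6446, 200/242 = 0.8264 and 1. Allocation is 1:1, so 78, 100 and 121 per arm. Critical values are 0.0073, 0.0135 and 0.0200, or z of about 2.44, 2.21 and 2.05.

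**Step 1: Type I error of Table 6.** Under the null, the three z statistics are jointly normal with correlation √(tᵢ/tⱼ). The cumulative spend is the probability of crossing at any look so far.

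| | Look 1 | Look 2 | Final |
|---|---|---|---|
| Incremental, computed | 0.0073 | 0.0087 | 0.0100 |
| Incremental, listed | 0.0073 | 0.0083 | 0.00935 |
| Cumulative, computed | 0.0073 | 0.0160 | 0.0259 |
| Cumulative, listed | 0.0073 | 0.0156 | 0.025 |

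At the rounding limits of the critical values the total runs from 0.02586 (0.00725/0.01345/0.01995) to 0.02602 (0.00735/0.01355/0.02005), so rounding is not the cause.

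**Step 2: which column is wrong?** The documents do not settle it. Two readings fit part of the table:

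- *Spend and looks right.* The function 1−Φ(1.96/√t) at the stated looks gives cumulative 0.0073, 0.0155 and 0.025, nearly the listed column. Solving for the listed spend gives critical values 0.0073, 0.0131 and 0.0190, so the last two printed values are too large.
- *Spend and critical values right.* Lan-DeMets O'Brien-Fleming spending, 2(1−Φ(2.2414/√t)), equals 0.0073 and 0.0156 at t = 0.698 and 0.859, which is about 169 and 208 subjects. There Table 6's critical values give cumulative 0.0073, 0.0156 and 0.0250, so the look times are wrong. At the stated looks, Lan-DeMets would spend 0.0052, 0.0137 and 0.025, with critical values 0.0052, 0.0121 and 0.0207.

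**Step 3: Table 7.** Expected N is 156p₁ + 200p₂ + 242(1−p₁−p₂). For 40% vs 60%, Table 7's own entries give 156×0.44 + 200×0.22 + 242×0.34 = 194.9, its stated 195. Power is 0.44 + 0.22 + 0.19 = 0.85. So that row is internally consistent. The stopping probabilities were then computed by exact binomial enumeration with a continuity-corrected z test:

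| Control vs treatment | Look 1: stated / computed | Look 2: stated / 0.0135 / 0.0083 | Final: stated / 0.0135 / 0.0083 | Expected N: stated / 0.0135 / 0.0083 |
|---|---|---|---|---|
| 30 vs 50% | 0.48 / 0.479 | 0.19 / 0.235 / 0.189 | 0.19 / 0.145 / 0.188 | 193 / 190.9 / 192.9 |
| 40 vs 60% | 0.44 / 0.445 | 0.22 / 0.258 / 0.213 | 0.19 / 0.150 / 0.192 | 195 / 192.9 / 194.8 |
| 50 vs 70% | 0.48 / 0.479 | 0.19 / 0.235 / 0.189 | 0.19 / 0.145 / 0.188 | 193 / 190.9 / 192.9 |
| 60 vs 80% | 0.56 / 0.555 | 0.18 / 0.230 / 0.180 | 0.16 / 0.117 / 0.164 | 187 / 184.6 / 186.7 |
| 70 vs 90% | 0.70 / 0.704 | 0.16 / 0.194 / 0.159 | 0.10 / 0.069 / 0.103 | 175 / 173.3 / 174.8 |

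Over all 15 stopping cells the largest miss is 0.050 with 0.0135 and 0.007 with 0.0083. For Fisher's test it is 0.051 and 0.0095. Thresholds from 0.0083 to about 0.009 fit equally well. Pooled z and unadjusted logistic Wald miss by about 0.07 with either threshold. A likelihood ratio test was also tried, and none of the five tests fits with 0.0135. With 0.0135, total power under the continuity-corrected test is 0.859, 0.853, 0.859, 0.902 and 0.967, against the stated 0.86, 0.85, 0.86, 0.90 and 0.97.

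**Step 4: exact Type I error of Table 6's values by test** (unadjusted, null rates 30% to 70%). Logistic Wald gives 0.0252 to 0.0260, pooled z 0.0263 to 0.0282, and Fisher or continuity-corrected 0.018 to 0.020. The covariate-adjusted model of 9.7.1 was not computed.

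**The case against.** The strongest objection is that these tables govern nothing in this study. The SAP supersedes the protocol's statistical section where they differ substantially, the double-blind phase was not run here, and SAP 4.11 records that no formal interim analysis took place. That stands: no result changes, and it limits the weight of the point.

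Second, 0.0259 is a large-sample figure. With a Fisher or continuity-corrected test, the two that come closest to Table 7, the 2.5% limit holds. This also stands in part. But 9.7.1 plans a logistic model, and its unadjusted Wald form exceeds 0.025 at every null rate tried, if only by 0.0002 to 0.0010.

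Third, the looks are only approximate, and a spending approach can recompute boundaries at the information actually reached. Neither document says this will be done, and 9.7.1 ties the test to the tabulated values. Table 7 labels its columns 156, 200 and 242. Agreement within Table 6 needs looks 13 and 8 subjects later.

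Fourth, the idea that 0.0083 was used as a threshold is an inference, since the documents name no test behind Table 7. That is so. The mismatch with 0.0135 does not depend on the explanation.

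**Conclusion.** The concern holds. At the stated looks and under joint normality, Table 6's critical values spend 0.0259 against the listed 0.025, an excess of 0.09 percentage points. Table 7's second-look and final-look columns are off by about 3 to 5 points from the Table 6 rule, and its expected N is about 2 too high. Total power still meets 85% with Table 6's values as printed.

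Whether Type I error really exceeds 0.025 depends on the test, and the adjusted model was not evaluated. The use of 0.0083 at the second look is a likely explanation, not an established one. The consequence is confined to the protocol as written and to any reuse of the boundaries; the documents do not say whether they are reused.

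**What to change.** Make look timing, spend and critical values agree with a total of at most 0.025. Name the spending function, and say whether boundaries are recomputed at the actual look sizes. Four ways to do it, with power at 40% vs 60%:

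| Option | Critical values | Normal-theory total | Power: Wald / continuity-corrected |
|---|---|---|---|
| (a) Keep the looks and the listed spend | 0.0073 / 0.0130 / 0.0190 | 0.02495 | 0.86 / 0.83 |
| (b) Keep the looks and the first two values | 0.0073 / 0.0135 / 0.0187 | 0.02496 | 0.86 / 0.83 |
| (c) Keep the looks, use Lan-DeMets O'Brien-Fleming | 0.0052 / 0.0121 / 0.0206 | 0.0249 | 0.88 / 0.853 |
| (d) Keep the values, move the looks to about 170 and 208 | 0.0073 / 0.0135 / 0.0200 | 0.02496 | 0.87 / 0.85 |

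Option (b) follows no named spending function. Option (d) delays the looks: at 40% vs 60%, expected N rises from 192.9 to 196.6 (continuity-corrected) or from 188.1 to 194.6 (Wald).

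A normal-theory total below 0.025 does not settle the exact error. The same enumeration with unadjusted Wald gives at most about 0.0250 under (a) and 0.0247 under (b), but up to 0.0269 under (c) and 0.0259 under (d). The chosen boundaries should therefore be checked with the planned test.

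Then rerun Table 7 with those thresholds and the planned logistic test, name the test, and restate power and expected N. The cost is a few entries in Table 6 and a rerun of Table 7. More subjects would be needed only if (a) or (b) is paired with a Fisher or continuity-corrected test, where power falls to about 0.83, below the stated 85%.

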**Table 6: Interim Analysis Variables**

Analysis	# Subjects who completed the study anytime within 24 hours of study drug administration	One-sided Critical Value	Error Spend	Cumulative Error Spend
Interim 1	156 subjects	0.0073	0.0073	0.0073
Interim 2	200 subjects	0.0135	0.0083	0.0156
Final	242 subjects	0.0200	0.00935	0.025

In the double-blind group a Data Monitoring Committee (DMC) will be assembled to review the safety and efficacy data at various intervals of the study. Only the unblinded DMC will be privy to these interim analyses and may recommend the trial stop for early success or safety findings.

Likewise, at each interim analysis, Bayesian predictive probabilities for success at the maximum (N=242) sample size will be calculated. If the predictive probability of success is < 5%, then the DMC may recommend the trial stops for futility. These are non-binding futility analyses, e.g., the Type I error = 2.5% even without these futility analyses. The Bayesian predictive probabilities will use non-informative Beta (1/2, 1/2) priors for both unknown response rates and be conducted using the methodology described in Saville et al., 2014 (Clinical Trials).

## 9.5 Sample Size Calculation and Power Considerations

The double-blind sample size was constructed to offer at least 85% power with a 20% effect.

Table 7 shows the power for a control group response rates ranging from 30% to 70% and assuming a 20% improvement in the treatment group.

**Table 7: O'Brien-Fleming Power and Sample Size Power Calculation**

Control Response %	Treatment Response %	Probability of Stopping at 156 Subjects	Probability of Stopping at 200 Subjects	Probability of Stopping at 242 Subjects	Total Power	Expected N
0.3	0.5	0.48	0.19	0.19	0.86	193
0.4	0.6	0.44	0.22	0.19	0.85	195
0.5	0.7	0.48	0.19	0.19	0.86	193
0.6	0.8	0.56	0.18	0.16	0.90	187
0.7	0.9	0.70	0.16	0.10	0.97	175

Two-hundred and forty-two subjects with the described O'Brien-Fleming stopping rules ensures 85% power in the scenario of 60% vs. 40% and increases for other scenarios with 20% effect sizes.

Using the futility rules based upon predicted probabilities, when control and treatment group response rates are equal, the probability of early stopping is 88% and expected sample size is 171.

## 9.6 Study Population

The **Screened Set** will consist of all subjects who have signed an informed consent.

The **Safety Set** will consist of all subjects who have received ganaxolone IV solution.

The **Modified Intent-to-Treat (mITT) Set** includes all subjects who received at least one dose of the study drug and who provided any post study drug initiation seizure/status outcome data.

The **Per-Protocol Set** will consist of all subjects in the mITT population without major protocol violations. The Per Protocol population is for supportive efficacy analysis. Major protocol violations will be defined prior to database lock.

The **Completer Set** will consist of all subjects in the mITT who have completed the final scheduled primary assessment for the study.

The **Pharmacokinetic Set** will consist of all subjects in the Safety Set for whom the primary pharmacokinetic data is considered sufficient and interpretable.

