- a. Pre-dose (screening) and 36-hours (+/- 1-hour) after study drug initiation,
- b. Time of study drug discontinuation, either at the end of the study drug taper or if the study drug administration is stopped without a taper and
- c. 24-hours (+/- 1-hour) after study drug discontinuation.
- d. Week 2, 3, and 4 follow-up visits (in-person or via telephone call).
- e. If possible, for subjects who early terminate from the study, collect at the time early termination is being considered and as close as possible to the end of the study drug administration.
- f. Any time, if medically indicated, per investigator's judgment.

CGI-I is collected at:

- a. Within the first 2 hours of study drug initiation and 36-hours (+/- 1-hour) after study drug initiation,
- b. Time of study drug discontinuation, either at the end of the study drug taper or if the study drug administration is stopped without a taper and
- c. 24-hours (+/- 1-hour) after study drug discontinuation.
- d. Week 2, 3, and 4 follow-up visits (in-person or via telephone call).
- e. If possible, for subjects who early terminate from the study, collect at the time early termination is being considered and as close as possible to the end of the study drug administration.
- f. Any time, if medically indicated, per investigator's judgment.

14. Modified Rankin Scale (MRS) should be collected at:

- a. Time of study drug discontinuation, either at the end of the study drug taper or if the study drug administration is stopped without a taper and
- b. 24-hours (+/- 1-hour) after study drug discontinuation.
- c. Week 2, 3 and 4 follow-up visits (in-person or via telephone call).
- d. If possible, for subject's who early terminate from the study, collect at the time early termination is being considered and as close as possible to the end of the study drug administration.
- e. Any time, if medically indicated, per investigator's judgment.

15. Status Epilepticus and Seizure Questions should be collected at:

- a. 15-minutes (+/- 5-min), 30-, 60-minutes (+/- 15-min), 2-, 4-, 6-, 8-, 10-, 12-, 18- (+/- 30-min), and 24- and 36-hours (+/- 1 hour) after study drug initiation,
- b. Time of study drug discontinuation, either at the end of the study drug taper or if the study drug administration is stopped without a taper and
- c. 24-hours (+/- 1-hour) after study drug discontinuation.
- d. Week 2, 3, and 4 follow-up visits (in-person or via telephone call).

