- e. If possible, for subjects who early terminate from the study, collect at the time early termination is being considered and as close as possible to the end of the study drug administration.

Assessment questions:

1. Is the subject in SE currently?
2. Was the subject in SE since the previous assessment?  
(Note: N/A for the 15-minute timepoint)
3. Is the subject having seizures currently?
4. Did the subject have seizures since the previous assessment?  
(Note: N/A for the 15-minute timepoint)
5. Have any new\* AEDs been initiated since the last assessment?  
(Note: “New” refers to any AED that has not already been used to treat the current episode of SE)
6. If a new AED was initiated, was it to treat the current seizure/SE episode or initiated prophylactically (e.g., for transition/bridging), or other reason?  
(Note: “Prophylactic” refers to any elective/transitional/bridging AED therapy that is not indicated to treat seizure/EEG abnormal activity at this time or since the last assessment)

Record any new AEDS on the concomitant eCRF page.

16. Intubation Question will be collected for subjects who are intubated either prior to study drug initiation or anytime through the end of the in-patient follow-up day:

- a. 18- (+/- 30-min), 24-, and 36-hours (+/- 1 hour) after study drug initiation,
- b. Time of study drug discontinuation, either at the end of the study drug taper or if the study drug administration is stopped without a taper and
- c. 24-hours (+/- 1-hour) after study drug discontinuation.

Assessment point:

1. Per your evaluation has the subject’s medical condition improved enough to warrant considering extubation?

17. Adverse events (AEs) and Concomitant medications: AE’s will be collected throughout the study via non-direct questioning. Concomitant medications will be collected during the same time period however, the collection requirements will differ depending on the subject’s treatment progression as defined below.

- a. All adverse events and associated concomitant medications will be collected through the in-patient follow-up day.
- b. IV anesthetic agents (midazolam, propofol, thiopental, pentobarbital, or ketamine) administered during the study drug treatment period and the in-patient follow-up day should be followed through the week 4 visit/contact.

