#### **5.2 Concomitant Treatment**

Concomitant treatment refers to all treatment taken between the date of the first dose of study drug and the end of the follow-up period, inclusive. However, the collection requirements will differ depending on the subject's treatment progression as defined below.

- All concomitant medications will be collected through the in-patient follow-up day
- During the weekly follow-up visits, only concomitant medications associated with ongoing AEs and new AEs assessed by the investigator to be related to study drug will be recorded
- All concomitant medications associated with SAEs regardless of relationship to study drug will be recorded from the time of study drug initiation through the last follow-up visit/contact
- In addition, for subjects who stop study drug administration without a taper but continue with the follow-up visits, any IV anesthetic agents (midazolam, propofol, thiopental, pentobarbital, or ketamine) that were started on the in-patient follow-up day should be followed through the last follow-up visit/contact
- At the time that early termination from the study is being considered, prior to discontinuation as much information as is available should be recorded on the concomitant medications associated with ongoing AEs/SAEs and new AEs/SAEs, especially those that may have led to the early termination

Concomitant treatment information must be recorded on the appropriate eCRF page. For some of the concomitant medications only the highest dose administered will be required in the eCRF. Reference the eCRF Completion Guidelines for guidance

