### **5.2.2 Prohibited Treatment**

As per the exclusion criterion in Section 4.2, the only allowable concurrent 2nd line IV AED therapies to treat the current episode of SE are fosphenytoin/phenytoin, valproic acid, levetiracetam, lacosamide, or brivaracetam. Administering fosphenytoin and/or phenytoin will be counted as one (1) AED. These drugs can be used alone or in combination with each other. If the subject is receiving oral AED therapy to manage a subject's chronic medical condition, for example, epilepsy, migraine, or neuropathic pain, that therapy is acceptable and should continue unchanged, if feasible and medically justified. This prophylactic treatment does not count towards the SE treatment failures required to qualify for this study. If any of these oral AED medications had to be interrupted around the time of the current SE episode, it is recommended that they would be re-started 10 hours after study drug initiation, if medically acceptable. Also, subjects who have been enrolled in another clinical study for SE are required to have a reasonable expectation that the other investigational drug has been cleared from their system, that is, that five half-lives have elapsed. Subjects on IV AEDs that are standard of care can be enrolled in the study. Subjects who have taken exogenous allopregnanolone or ganaxolone previously are not eligible for the study.

If a subject progresses at any time during the study to an IV anesthetic drug (a 3rd line treatment; e.g. midazolam, propofol, thiopental, pentobarbital, or ketamine and/or 4th line treatment; e.g., immunosuppressants, magnesium) for seizure suppression, study drug administration will be discontinued, however the subject will continue with the in-patient follow-up day and the week 2, 3, and 4 follow-up visits.

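### The primary-analysis set requires post-dose seizure/status data that the primary outcome does not use, and no rule classifies deaths or missing outcomes before 24 hours

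*Protocol*

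**What the plan says.** Protocol 9.6 sets two conditions for the mITT set: the subject was dosed, and the subject is one "who provided any post study drug initiation seizure/status outcome data". Section 9.7.1 states: "The primary efficacy analysis will be conducted over the mITT Set". The same section defines the endpoint as "the number of subjects who did not require an IV anesthetic drug" for SE in the first 24 hours.

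The endpoint and the entry condition draw on different records. The synopsis, under Safety and Assessments, handles anesthetics with concomitant medication: it names "IV anesthetic agents (midazolam, propofol, thiopental, pentobarbital, or ketamine) administered during the study drug treatment period and the in-patient follow-up day" and asks that they be followed to Week 4. Section 5.2 adds: "All concomitant medications will be collected through the in-patient follow-up day". The SE and Seizure Questions (section 7.2.2.6) ask about SE, seizures and new AEDs, and have no anesthetic item.

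Neither document defines seizure/status outcome data. Neither says whether anesthetic use counts as such data, or how a dosed subject without it is classified. Protocol 9.3 leaves missing data to the SAP, but the imputation rules in SAP 4.4 cover only adverse-event and medication dates.

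The SAP covers the open-label group alone. It moves the double-blind phase to a separate phase 3 study (section 1), defines the Safety Population by dosing only (4.1), and uses it for all efficacy summaries without inferential tests (4.8). Its primary endpoint (4.2.1) matches the protocol's.

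**The concern.** A condition applied after randomisation and dosing can remove subjects for reasons linked to how they fared. Those most likely to have no seizure/status record are those who die or leave very early. For early terminators, the synopsis asks for the questions only where possible. If one arm loses more such subjects than the other, the response rates are no longer compared between the groups that were randomised. The statement in 9.7.1 that one-sided type I error stays within 0.025 assumes that exclusions are unrelated to arm and outcome.

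A second gap sits beside it. Read literally, the endpoint counts a subject who dies before 24 hours without an anesthetic as a success. The SAP endpoint carries the same wording, so this gap reaches the open-label summary as well.

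**Working it through.** **1. How often could the exclusion occur?** The synopsis (item 15) and Table 1 footnote r schedule the questions as follows:
- 12 times after initiation: 15, 30 and 60 minutes, then 2, 4, 6, 8, 10, 12, 18, 24 and 36 hours;
- once at drug stop, described as "Time of study drug discontinuation, either at the end of the study drug taper or if the study drug administration is stopped without a taper";
- once 24 hours after drug stop;
- at Weeks 2, 3 and 4.

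That makes 12 + 1 + 1 + 3 = 17 collections. For a subject who progresses to an anesthetic, section 5.2.2 says that "study drug administration will be discontinued, however the subject will continue with the in-patient follow-up day", and the weekly visits follow. Even a subject who stops drug before 15 minutes has at least 1 + 1 + 3 = 5 later collections. The condition asks for any datum and sets no time limit, so exclusion requires every one of these to be missing and no other status data, such as EEG, to count. The exposed subjects are mainly very early deaths and withdrawals with nothing recorded.

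**2. Effect on one arm's rate.** Inputs: 242 subjects allocated 1:1 give 121 per arm; the 60% treatment rate in the Table 7 scenario of 40% versus 60% gives 0.60 × 121 = 72.6, taken as 73 responders. The numbers excluded are assumptions. The rate after dropping m failures is 73/(121 − m).

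| m (assumed) | Rate | Change (points) |
|---|---|---|
| 0 | 73/121 = 60.3% | – |
| 1 | 73/120 = 60.8% | +0.5 |
| 3 | 73/118 = 61.9% | +1.5 |
| 5 | 73/116 = 62.9% | +2.6 |

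**3. Effect on the test.** The plan's own power was reproduced first, by simulating looks at 78, 100 and 121 per arm with the Table 6 critical values (0.0073, 0.0135, 0.0200) and a one-sided Fisher test. Total power for control rates of 30% to 70% was 0.860, 0.852, 0.858, 0.902 and 0.968, against 0.86, 0.85, 0.86, 0.90 and 0.97 in Table 7. At 40% versus 60%, the split between second interim and final differs somewhat (0.257 and 0.150 against 0.22 and 0.19); the total agrees.

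Next, an assumed share q of failures was dropped. At a 40% response rate, q = 5% in one arm is 0.05 × 0.60 × 121 = 3.6 subjects.

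| q (assumed) | 40% in both arms, treatment failures dropped: one-sided rejection | 40% vs 60%, control failures dropped: power | 40% vs 60%, same q in both arms: power |
|---|---|---|---|
| 0 | 0.019 | 0.853 | 0.852 |
| 5% | 0.030 | 0.788 | 0.833 |
| 10% | 0.044 | 0.712 | 0.818 |

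Fisher's test stands in here for the covariate-adjusted logistic model of 9.7.1. Type I error is inflated when the loss differs between arms. Step 1 suggests that even q = 5% in a single arm would be high.

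**4. The open-label endpoint.** The protocol enrols up to about 30 open-label subjects. If 30 are treated, each death before 24 hours without an anesthetic moves the overall rate by 1/30 = 3.3 points, depending on whether it is counted as success or failure. The move is larger within a dose cohort.

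**The case against.** The strongest reply is that the clause touches no analysis this study will run. The SAP supersedes the protocol's statistics where they differ, drops the logistic comparison (5.1), and summarises efficacy on a population with no outcome-data condition. That stands. SAP 4.4 still mentions mITT and per-protocol displays by randomised treatment, but SAP 4.1 defines neither set and no subject was randomised.

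A second reply is that an anesthetic given for SE could itself count as status outcome data, in which case a known anesthetic failure is already in the set. This is a fair reading, but the text does not state it, and it does not help subjects who die or withdraw early without an anesthetic.

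A third is that the sizes above are assumed. They are; the documents give no exclusion rate.

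A reader might also infer that anyone who escalates before the 15-minute question is lost. The documents do not support that: such subjects stay in follow-up, and any later answer admits them. Medical staff must also be present for at least the first 3 hours (section 6.2.3), and a life expectancy under 24 hours is an exclusion criterion, so blank records should be few.

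**Conclusion.** The clause is a real but small defect in the protocol's stated primary analysis. It makes entry to the primary set depend on data collected after randomisation that the endpoint does not need; it can depend on outcome, and it brings no benefit. Its likely effect is a fraction of a point to a few points on one arm's rate, and that range rests on assumed exclusions of 1 to 5 failures among 121 subjects.

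Two stronger conclusions are tempting but not supported. One is that this study's reported efficacy is biased by the clause: the open-label summaries use the Safety Population, so it is not. The other is that the sample size or power in Table 7 is wrong: with every dosed subject kept, simulated power at 40% versus 60% is 0.852, as planned. The clause matters for the protocol's double-blind comparison and for any phase 3 plan that copies the definition; that plan is not among the documents. The missing rule for deaths before 24 hours is separate, and does apply to the SAP's open-label endpoint.

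**What to change.** In Protocol 9.6, define the primary set as all randomised subjects who started study drug, and delete the seizure/status-data condition. Carry this definition into the phase 3 plan.

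In Protocol 9.7.1 and SAP 4.2.1, state that death before 24 hours counts as non-response, and that withdrawal or a missing 24-hour anesthetic outcome counts as non-response in the primary summary. The two changes belong together: if the data condition is removed alone, a very early death without an anesthetic enters the set and, on a literal reading, counts as a success.

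The leftover mITT and per-protocol line in SAP 4.4 can be deleted at the same time.

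The cost is one clause and one classification rule. The planned 242 subjects and the power are unchanged, and no new data are collected. Response rates will be slightly less favourable.
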